5.8.2. Analysis of Adverse Events of Special Interest

- Treatment-emergent adverse events of special interest (AESI), as listed in Section 4.8.1.2, will be presented by SOC and PT. AESI are defined by SMQ, CMQ, and dedicated e-CRF as described in Appendix 10.3 .

The following variables will also be tabulated for infusion reactions TEAEs:

- Intensity of the event (mild, moderate, severe or very severe);
- Number of events divided by the number of study treatment administrations received in respective treatment periods;
- Time from first study treatment administration (DBTP or OLTP depending on the analysis) to first infusion reaction;

5.8.3. Clinical Laboratory Measurements

For respective treatment period (DBTP and OLTP), clinical laboratory parameter actual values (quantitative) and change from baseline values will be descriptively summarized at baseline and each post-baseline visit (collected up to the day of last dose of study treatment +28 days) by at least patient number, mean, median, Q1, Q3, SD, minimum and maximum. Clinical laboratory parameters mean changes from baseline, with the corresponding SE, can be plotted at each visit in the case results warrant further investigation. These parameters will be presented by the biological functions defined in Section 4.8.2. For glucose, only fasting samples will be included in the summaries.

Individual patient laboratory parameter measurements will be additionally evaluated by PCSV criteria (See Appendix 10.4), specifically identifying patients with at least one post-baseline measurement that meets the PCSV criteria within the respective TEAE periods. These laboratory parameters will be presented by the biological functions defined in Section 4.8.2. The incidence of PCSVs at any time during the respective TEAE periods will be summarized regardless of the baseline level, and again according to the following baseline categories:

- Normal (according to PCSV criterion/criteria)/missing
- Abnormal according to PCSV criterion or criteria

Patient listings of laboratory measurements that meet PCSV criteria will be provided for the report appendix. For those laboratory parameters that don't have an associated PCSV criteria, similar summary tables can be provided based on measurements outside the central laboratory normal ranges, if applicable.

Drug-induced liver injury

For respective treatment period (DBTP and OLTP), an evaluation of drug-induced serious hepatotoxicity (eDISH) with the graph of distribution of peak values of ALT versus peak values of total bilirubin will also be presented using post-baseline values during respective TEAE periods. Note that the ALT and total bilirubin values are presented on a logarithmic scale. The graph will be divided into 4 quadrants with a vertical line corresponding to 3 x ULN for ALT and a horizontal line corresponding to 2 x ULN for total bilirubin.

Patient listing of possible Hy's law cases identified by treatment group (i.e., patients with any elevated ALT > 3 x ULN, and associated with an increase in bilirubin > 2 x ULN, concomitantly or not) with ALT, AST, ALP, total bilirubin, and if available direct and indirect bilirubin will be provided.

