7. STUDY TREATMENTS

7.1. Investigational and Reference Treatments

Evinacumab or placebo IV infusion.

In the DBTP, eligible patients will be enrolled to receive an IV dose of evinacumab 15 mg/kg Q4W or matching placebo, starting on day 1. The last dose of double-blind study drug will be at week 20.

In the open-label portion of the study, patients will receive

- Evinacumab at 15 mg/kg IV Q4W starting at week 24 (day 169) with the last dose at week 44 (day 309)

Dosing should fall within a window of ± 7 days; if >14 days has passed, skip the dose and return to the original schedule.

Instructions on dose preparation and administration are provided in the pharmacy manual.

Instructions on management of infusion reactions are provided in Section 7.5.1.

Sterile alirocumab drug product will be supplied at a concentration of 150 mg/mL in a prefilled pen for patients from study R727-CL-1628 who enroll in this study.

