10.4.4.2. Other Safety

Definitions

The following definitions will be applied to laboratory parameters and vital signs:

- The potentially clinically significant value (PCSV) criteria are defined as abnormal values considered medically important by the sponsor according to predefined criteria/thresholds based on literature review and defined by the sponsor for clinical laboratory tests and vital signs. PCSV criteria will be provided in the SAP.
- PCSV criteria will determine which patients had at least 1 PCSV during the respective TEAE periods (double-blind and open-label), taking into account all evaluations performed during the respective TEAE periods, including unscheduled or repeated evaluations. The number of all such patients will be the numerator for the PCSV percentage.
- Double-blind treatment period: The treatment period used for the quantitative analysis of laboratory and vital signs data in the double-blind period is defined from the day after the first dose of double blind study treatment to the day of the last dose of double-blind study treatment + 28 days for those patients not proceeding into the OLTP, or up to the day of the first dose of open-label study treatment administration for those patients proceeding into the OLTP.
- Open-label treatment period: The treatment period used for quantitative analysis of laboratory and vital signs data in the open-label study period is defined from the day after the first dose of open-label study treatment to the day of the last dose of open-label study treatment + 28 days.

Analysis

Summary statistics of all laboratory variables (including lipid HDL-C) and all vital signs parameters (raw data and changes from baseline) will be calculated for each protocol scheduled visit assessed during the respective treatment periods. For selected parameters, mean changes from

baseline with the corresponding SE may be plotted over time (at same time points) in each treatment group.

The incidence of PCSVs at any time during the respective TEAE periods will be summarized regardless of the baseline level, and again according to the following baseline categories:

- Normal/missing
- Abnormal according to PCSV criterion or criteria

For laboratory parameters for which a PCSV criterion is not defined, similar table(s) using the normal range will be provided, regardless of baseline level.

Listings will be provided with flags indicating the laboratory values meeting PCSV criteria.

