10.4.4.2. Other Safety

Definitions

The following definitions will be applied to laboratory parameters and vital signs:

- The potentially clinically significant value (PCSV) criteria are defined as abnormal values considered medically important by the sponsor according to predefined criteria/thresholds based on literature review and defined by the sponsor for clinical laboratory tests and vital signs. PCSV criteria will be provided in the SAP.
- PCSV criteria will determine which patients had at least 1 PCSV during the respective TEAE periods (double-blind and open-label), taking into account all evaluations performed during the respective TEAE periods, including unscheduled or repeated evaluations. The number of all such patients will be the numerator for the PCSV percentage.
- Double-blind treatment period: The treatment period used for the quantitative analysis of laboratory and vital signs data in the double-blind period is defined from the day after the first dose of double blind study treatment to the day of the last dose of double-blind study treatment + 28 days for those patients not proceeding into the OLTP, or up to the day of the first dose of open-label study treatment administration for those patients proceeding into the OLTP.
- Open-label treatment period: The treatment period used for quantitative analysis of laboratory and vital signs data in the open-label study period is defined from the day after the first dose of open-label study treatment to the day of the last dose of open-label study treatment + 28 days.

Analysis

Summary statistics of all laboratory variables (including lipid HDL-C) and all vital signs parameters (raw data and changes from baseline) will be calculated for each protocol scheduled visit assessed during the respective treatment periods. For selected parameters, mean changes from baseline with the corresponding SE may be plotted over time (at same time points) in each treatment group.

The incidence of PCSVs at any time during the respective TEAE periods will be summarized regardless of the baseline level, and again according to the following baseline categories:

- Normal/missing
- Abnormal according to PCSV criterion or criteria

For laboratory parameters for which a PCSV criterion is not defined, similar table(s) using the normal range will be provided, regardless of baseline level.

Listings will be provided with flags indicating the laboratory values meeting PCSV criteria.

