4.8.1. Adverse Events Variables

The period of safety observation starts from the time when the patient gives informed consent and continues into the following periods:

- The PRE-TREATMENT period is defined from the day the ICF is signed to the day before the first dose of double-blind study treatment administration.
- The double-blind treatment-emergent adverse event (TEAE) period is defined from the day of the first dose of double-blind study treatment administration to the day of the last dose of double-blind study treatment administration + 168 days (24 weeks) for those patients not proceeding into the OLTP, or up to the day before the first dose of open-label study treatment administration for those patients proceeding into the OLTP

The double-blind TEAE period will include:

- The TREATMENT period is defined from the day of first double-blind study treatment administration up to the day of last double-blind study treatment administration + 35 days. For patients entering into the OLTP, the treatment period will be truncated at the day before the first dose of open-label study treatment administration.
- The RESIDUAL TREATMENT period is defined from the day of last double-blind study treatment administration + 36 days up to the day of last double-blind study treatment administration + 168 days (24 weeks), or up to the day before first dose of open label study treatment administration, whichever is earlier.
- The open-label treatment-emergent adverse event (TEAE) period is defined from the day of the first open-label study treatment administration to the day of the last open-label study treatment administration + 168 days (24 weeks). For patients entering the open-label study R1500-CL-1719, the TEAE period will be truncated at the day before first study treatment administration in R1500-CL-1719.

The open-label TEAE period will include:

- The TREATMENT period is defined from the day of first open-label study treatment administration up to the day of last open-label study treatment administration + 35 days.
- The RESIDUAL TREATMENT period is defined from the day of last open-label study treatment administration + 36 days up to the day of last open-label study treatment administration + 168 days (24 weeks).

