5.8. Analysis of Safety Data

The summary of safety results will be presented separately for the DBTP and OLTP, unless otherwise noted. Safety summaries for the DBTP will be presented by treatment groups (evinacumab, placebo) containing patients from the double-blind safety analysis set. Safety summaries for the OLTP will be presented by all patients and by treatment group in DBTP (i.e.,

evinacumab, placebo), for patients in the open-label safety analysis set. No formal inferential testing will be performed for either period. Summaries will be descriptive in nature.

General common rules

All safety analyses will be performed, unless otherwise specified, using the following common rules:

- Safety data in patients who do not belong to the safety analysis set (i.e., exposed but not randomized) will be listed separately.
- PCSV values are defined as abnormal values considered medically important by the Sponsor according to predefined criteria/thresholds based on literature review and defined by the Sponsor for clinical laboratory tests and vital signs (PCSV version dated January 2009 [Appendix 10.4]). Considering that the threshold defined in the PCSV list for monocytes and basophils can be below the ULN, the following PCSV criterion will be used for the PCSV analysis of monocytes and basophils:
 - PCSV criterion for monocytes: >0.7 Giga/L or $>ULN$ (if $ULN \geq 0.7$ Giga/L).
 - PCSV criterion for basophils: >0.1 Giga/L or $>ULN$ (if $ULN \geq 0.1$ Giga/L).
- PCSV criteria will determine which patients had at least 1 PCSV during the respective TEAE periods, taking into account all evaluations including unscheduled or repeated evaluations.
- The treatment-emergent PCSV denominator by treatment group for a given parameter will be based on the number of patients assessed for that given parameter at least once during the respective TEAE periods.
- All measurements, scheduled or unscheduled, fasting or not fasting, will be assigned to Global Analysis Windows defined in Appendix 10.2 /Table 1 in order to provide an assessment for the screening visit through follow-up visit time points.
- For quantitative safety parameters including central laboratory measurements and vital sign scores, descriptive statistics will be used to summarize observed values and change from baseline values by visit.

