Demographics	X
Treatment:	
Concomitant Medications (including LMT and apheresis)	X
Query LMT Compliance	X
Efficacy:	
Lipid Panel ^{1,2}	X
Safety:	
Adverse Events	X
Physical Examination	X
Measured Height	X
Body Weight	X
Vital Signs (pulse rate, BP)	X
Electrocardiogram ³	X
Tanner stage ⁴	X
Laboratory Testing⁵:	
Hematology	X
Blood Chemistry	X
Creatine Phosphokinase	X
Hepatitis B Surface Antigen	X
Hepatitis C Antibody	X
Serum Pregnancy Test ⁶	X
Urine Pregnancy Test ⁶	
Sex Hormones ⁴	X
FSH	X
Urinalysis	X
TSH	X
DNA sample for HoFH genotyping	X
Other:	
Review of diet	X

Footnotes for Schedule of Events – Screening for Patients with No Run-in

1. Study assessments will be performed and blood samples will be collected before the dose of study drug in all patients. For patients undergoing apheresis: Study assessments will be performed and blood samples will be collected immediately before the lipid-apheresis procedure; study drug will be administered after the apheresis procedure.
2. Fasting sample will be collected for the lipid panel: total-C, calculated LDL-C, HDL-C, TG, non-HDL-C

3. ECG should be performed before blood samples are collected at visits requiring blood draws.
4. Assessment of Tanner Stage and sex hormones (includes luteinizing hormone, follicle stimulating hormone, estradiol, total testosterone) only applicable to patients <18 years old.
5. All laboratory samples should be collected before administration of study drug.
6. WOCBP only, confirm required contraception use and reminder pregnancy reporting

Schedule of Events – Baseline, Double-Blind Treatment Period, and Open-Label Treatment Period

Study Procedure	Double-Blind Treatment Period								Open-Label Treatment Period					
	2	3	4	5	6	7	8	9 End DBTP ¹⁴	10	11	12	13	14	15 End of OLTP
Day	1	15	29	57	85	113	141	169	197	225	253	281	309	337
Visit Window (Day)	±1	±3	±3	±3	±3	±5	±5	±1	±5	±5	±5	±5	±5	±5
Week	0	2	4	8	12	16	20	24	28	32	36	40	44	48
Baseline:														
Informed Consent	X ¹													
	X ¹													
Treatment:														
Randomization	X ¹													
Administer IV Double-Blind Study Drug	X ¹		X	X	X	X	X							
Administer IV Open-Label Study Drug								X ¹⁰	X	X	X	X	X	
Concomitant Medications (including LMT and apheresis)	X	X	X	X	X	X	X	X	X	X	X	X	X	X
Query LMT Compliance	X ¹	X	X	X	X	X	X	X	X	X	X	X	X	X
Efficacy:														
Lipid Panel ^{2,3}	X	X	X	X	X	X	X	X	X	X	X	X	X	X
Specialty Lipid Panel ^{2,4}	X		X	X	X	X		X		X		X		X
Safety:														

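### Open-label by-visit laboratory and vital-sign summaries stop 28 days after the last dose, exactly the planned gap to week 48, so compliant week-48 samples can be lost on timing alone

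*SAP*

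**What the plan says.** SAP 5.8.3 (laboratory) and 5.8.4 (vital signs) summarise observed values and changes from baseline at each post-baseline visit, for both treatment periods, using values "collected up to the day of last dose of study treatment +28 days". Protocol 10.4.4.2, in both protocol versions, agrees for the open-label end: "The treatment period used for quantitative analysis of laboratory and vital signs data in the open-label study period" runs from the day after the first open-label dose "to the day of the last dose of open-label study treatment + 28 days".

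Protocol 7.1 places the last open-label dose at week 44, day 309, and states: "Dosing should fall within a window of ± 7 days". The schedule of events (protocol Table 3; SAP Appendix 10.9) puts week 48 at day 337 and gives weeks 44 and 48 a visit window of ±5 days each. SAP Appendix 10.2, Table 1, assigns study days 323 to 350 to week 48.

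SAP 5.8 also has a general rule that assigns all measurements to these analysis windows. It is introduced by: "All safety analyses will be performed, unless otherwise specified, using the following common rules".

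**The concern.** The cut-off equals the planned interval from last dose to final on-treatment visit. A week-48 sample taken on target passes. One taken a day further from the dose fails, even when dose and visit both met their windows. Such a value would be missing from the week-48 mean, median and change from baseline because of calendar timing, not because the patient had stopped treatment.

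Week 48 is one of only three scheduled chemistry and hematology draws after the first open-label dose and within the open-label period (weeks 32, 40 and 48), and one of six vital-sign visits. With about 57 patients randomized, a handful of timing exclusions would show in the table. SAP 5.7.2.5 summarises open-label lipids at each scheduled visit with no stated 28-day limit, so one blood draw could contribute its LDL-C to a week-48 table while its ALT is dropped.

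**Working it through.** **Inputs**

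- Last open-label dose: day 309 (protocol 7.1).
- Week-48 visit: day 337 (schedule of events).
- Visit window: ±5 days at week 44 and at week 48 (schedule of events).
- Dosing window: ±7 days (protocol 7.1).
- Cut-off: last dose + 28 days, inclusive (SAP 5.8.3, 5.8.4; protocol 10.4.4.2).
- Week-48 analysis window: days 323 to 350 (SAP Appendix 10.2, Table 1).

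**Step 1. Planned gap.** 337 − 309 = 28 days. This equals the cut-off, so the margin is zero.

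**Step 2. Range of compliant gaps.**

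- Both visits ±5: shortest 332 − 314 = 18; longest 342 − 304 = 38.
- Dose ±7, visit ±5: shortest 332 − 316 = 16; longest 342 − 302 = 40.

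**Step 3. Day pairs beyond a limit.** Write the dose offset as a and the visit offset as b. The gap is 28 + b − a, so it exceeds 28 when b > a and exceeds 35 when b − a ≥ 8.

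| Windows | Pairs | Gap > 28 | Gap > 35 |
|---|---|---|---|
| Dose ±5, visit ±5 | 11 × 11 = 121 | (121 − 11)/2 = 55 | 3 + 2 + 1 = 6 |
| Dose ±7, visit ±5 | 15 × 11 = 165 | sum of (b + 7) for b = −5 to 5 = 77 | 1 + 2 + 3 + 4 + 5 = 15 |

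If the dose falls on day 309, visits on days 338 to 342 are excluded. If the visit falls on day 337, any dose before day 309 excludes it.

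**Step 4. Does another rule bring these values back?**

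- In-window week-48 visits fall on days 332 to 342, all within 323 to 350, so the SAP itself labels them week 48.
- The general windowing rule in SAP 5.8 yields to anything specified otherwise, and 5.8.3 and 5.8.4 do specify otherwise, by date of collection.
- For patients who complete the open-label period, the first follow-up window starts at day 351, so an excluded sample does not reappear at a later visit.

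**Step 5. What is not affected.** PCSV incidence, the PCSV listings and the plot of peak ALT against peak bilirubin use the treatment-emergent periods, not the 28-day limit.

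**The case against.** The strongest reply is that 28 days is a deliberate, prespecified choice. It is one dosing interval, it matches the exposure definition (protocol 10.4.4.3; SAP 4.6), and protocol and SAP agree on it. The plan uses different limits for different purposes: 28 days here, 35 days for double-blind efficacy and the adverse-event treatment sub-period, and 168 days for treatment-emergent events. Those differences alone are not an inconsistency. That is fair: the 35-day figure shows only that the SAP accepts a longer on-treatment limit elsewhere. The deliberate-choice argument is weakened by the protocol's own double-blind rule, which for continuing patients runs to the first open-label dose and does not rely on 28 days. The week-48 end has no matching protection.

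It can also be argued that the text means the scheduled week-48 visit, whose nominal day is exactly +28. The limit, however, is worded by when values are collected, so an actual-day cut-off is the natural programming.

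Two further points stand. The pair counts weight all day combinations equally, and the loss approaches zero if the visit falls 28 days after the actual dose. The 165-pair set includes doses 6 or 7 days off target, which meet protocol 7.1 but not the ±5-day visit window; only the 121-pair set meets both rules. Nothing in the documents, however, ties the week-48 visit to the actual dose date. Protocol 5.1 lets apheresis run every 7 ± 1 or 14 ± 2 days, with sampling just before it and dosing after it. If each deviation applies per cycle, four weekly or two fortnightly cycles span 24 to 32 days, so gaps of 29 to 32 days can arise from following the protocol.

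**Conclusion.** The concern holds, as a minor point. The cut-off has zero tolerance, and compliant week-48 samples can be excluded although the SAP's own window assigns them to that visit. With both visits within ±5 days, 55 of 121 day pairs exceed the limit; with the ±7-day dosing window, 77 of 165 do. The number of patients affected depends on actual scheduling, which the documents do not give. The conclusion assumes the limit is applied to the actual collection day, as worded. The effect is confined to descriptive week-48 laboratory and vital-sign summaries in an uncontrolled period; no test, efficacy result or PCSV count depends on it.

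**What to change.** In SAP 5.8.3 and 5.8.4, state that for patients who received the week-44 dose the open-label by-visit summaries include all samples in the week-48 analysis window (days 323 to 350) taken before any first dose in R1500-CL-1719. Say explicitly that pre-dose samples on the day of that first dose are kept, because SAP 4.8.1 truncates at the day before it. Align protocol 10.4.4.2 in both versions, or record the departure as a row in SAP 1.2.4.

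A partial alternative is to borrow the SAP 4.8.1 treatment period, which runs "up to the day of last open-label study treatment administration + 35 days". That still leaves out 6 of 121 in-window pairs, or 15 of 165 with the ±7-day dosing window.

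As a clarification only, repeat in SAP 5.8.3 and 5.8.4 the protocol clause that double-blind data run to the first open-label dose for patients who continue.

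The cost is a sentence in each place and a small programming change. The full window admits values up to 350 − 304 = 46 days after the last dose, or 350 − 302 = 48 with the ±7-day dosing window, and these summaries lose their match to the 28-day exposure definition. No dose, visit or clinical rule changes.

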10.4. Criteria for Potentially Clinically Significant Values (PCSV)

Parameter	PCSV
Clinical chemistry	
ALT	By distribution analysis: >2 ULN and baseline \leq 2 ULN >3 ULN and baseline \leq 3 ULN >5 ULN and baseline \leq 5 ULN >10 ULN and baseline \leq 10 ULN >20 ULN and baseline \leq 20 ULN
AST	By distribution analysis: >2 ULN and baseline \leq 2 ULN >3 ULN and baseline \leq 3 ULN >5 ULN and baseline \leq 5 ULN >10 ULN and baseline \leq 10 ULN >20 ULN and baseline \leq 20 ULN
Alkaline Phosphatase	> 1.5 ULN and baseline \leq 1.5 ULN
Total Bilirubin	> 1.5 ULN and baseline \leq 1.5 ULN > 2 ULN and baseline \leq 2 ULN
Conjugated bilirubin	> 35% total bilirubin (when total bilirubin >1.5 ULN)
ALT and Total Bilirubin	ALT > 3 ULN and Total Bilirubin > 2 ULN and baseline ALT \leq 3 ULN or Total bilirubin \leq 2 ULN
CPK	> 3 ULN and \leq 5 ULN and baseline \leq 3ULN >5 ULN and \leq 10 ULN and baseline \leq 5 ULN >10 ULN and baseline \leq 10 ULN
Creatinine	\geq 150 μ mol/L (adults) \geq 30% from baseline \geq 100% from baseline
CLcr (mL/min) (Estimated creatinine clearance based on the Cockcroft-Gault equation)	\geq 15 - <30 (severe decrease in GFR) \geq 30 - < 60 (moderate decrease in GFR) \geq 60 - <90 (mild decrease in GFR) \geq 90 (normal GFR)
eGFR (mL/min/1.73m ²) (Estimate of GFR based on an MDRD equation)	\geq 15 - <30 (severe decrease in GFR) \geq 30 - < 60 (moderate decrease in GFR) \geq 60 - <90 (mild decrease in GFR) \geq 90 (normal GFR)

Parameter	PCSV
Uric Acid Hyperuricemia: Hypouricemia:	>408 µmol/L <120 µmol/L
Blood Urea Nitrogen	≥17 mmol/L
Chloride	<80 mmol/L >115 mmol/L
Sodium	≤129 mmol/L ≥ 160 mmol/L
Potassium	< 3 mmol/L ≥ 5.5 mmol/L
Glucose Hypoglycaemia Hyperglycaemia	≤ 3.9 mmol/L and < LLN ≥ 7 mmol/L (fasted); ≥ 11.1 mmol/L (unfasted)
HbA1c	>8%
Albumin	≤25 g/L
Hs-CRP	> 2 ULN or >10 mg/L, if ULN not provided
Hematology	
WBC	< 3.0 Giga/L (3000/ mm ³) (Non-Black) < 2.0 Giga/L (2000/ mm ³) (Black) ≥16.0 Giga/L (16000/ mm ³)
Lymphocytes	>4.0 Giga/L
Neutrophils	< 1.5 Giga/L (1500/ mm ³) (Non-Black) < 1.0 Giga/L (1000/ mm ³) (Black)
Monocytes	>0.7 Giga/L
Eosinophils	> 0.5 Giga/L (500/ mm ³) or > ULN if ULN ≥ 0.5 Giga/L
Hemoglobin	≤115 g/L (Male); ≤95 g/L (Female) ≥185 g/L (Male); ≥165 g/L (Female) Decrease from Baseline ≥15 g/L Decrease from Baseline ≥20 g/L
Hematocrit	≤0.37 v/v (Male) ; ≤0.32 v/v (Female) ≥0.55 v/v (Male) ; ≥0.5 v/v (Female)
RBC	≥6 Tera/L

Parameter	PCSV
Platelets	< 100 Giga/L (100 000/mm ³) ≥700 Giga/L (700000/mm ³)
Urinalysis	

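### Liver and CPK PCSV tables promise counts at any baseline and for abnormal baselines, but each tier's own baseline clause forces the abnormal-baseline count to zero

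*SAP*

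**What the plan says.** SAP 5.8.3 sets out two presentations of each laboratory PCSV within each TEAE period. The first covers all patients: "The incidence of PCSVs at any time during the respective TEAE periods will be summarized regardless of the baseline level". The second splits them by baseline into a normal/missing group and a group described as "Abnormal according to PCSV criterion or criteria". Protocol 10.4.4.2 has the same layout in both protocol versions supplied: incidence "will be summarized regardless of the baseline level, and again according to the following baseline categories".

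SAP Appendix 10.4 defines the criteria:

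- **ALT and AST:** five tiers at 2, 3, 5, 10 and 20 x ULN, running from ">2 ULN and baseline \leq 2 ULN" to ">20 ULN and baseline \leq 20 ULN".
- **ALP:** one tier, "> 1.5 ULN and baseline \leq 1.5 ULN".
- **Total bilirubin:** the same 1.5 x ULN tier, plus one at 2 x ULN built the same way.
- **CPK:** three bands (above 3 to 5, above 5 to 10, above 10 x ULN), each needing a baseline at or below the band's lower limit.
- **Conjugated bilirubin:** no baseline condition.
- **ALT combined with total bilirubin:** only one of the two baselines has to be within its limit.

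The common rules in SAP 5.8 take as denominator every patient assessed at least once for the parameter in the period. No section lifts the baseline clause for the all-patients or abnormal-baseline rows. SAP 6.3 deals only with missing baselines or missing conditions.

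**The concern.** A patient already above a cut-off at baseline cannot meet a criterion that requires a baseline at or below it. The abnormal-baseline row for that tier is then fixed at zero before any data are seen, and the all-patients row adds nothing to the normal/missing row.

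The table invites misreading. Other PCSVs, such as sodium, potassium, platelets, urea nitrogen and HbA1c, carry no baseline clause, so their abnormal-baseline rows do hold information. A liver or CPK row in the same format showing no events among patients with abnormal baselines would look reassuring, yet it could not have shown anything else.

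The criteria also feed the safety topics of interest. SAP Appendix 10.3 uses the Appendix 10.4 criteria as one source for hepatic disorders and names PCSV analyses for muscle events and CK elevation. The PCSV listing applies the same criteria, so it leaves out the same values.

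Such patients can enrol. The exclusions remove ALT, AST or CPK above 3 x ULN at screening but do not apply to randomization laboratory values, and they set no numeric limit for ALP or bilirubin. Lomitapide and mipomersen, which the protocol's introduction links to liver test increases, are permitted background therapy.

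**Working it through.** The plan gives no figure to reproduce here. The check is logical, with a grid calculation to show where the rules bite.

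**Step 1. One tier.** Let b be the baseline, p a post-baseline value and c the cut-off, all in multiples of ULN. The written rule is p > c and b ≤ c; the CPK bands add an upper limit on p. Abnormal at baseline for that tier means b > c. Both b > c and b ≤ c cannot hold, so the abnormal-baseline count is 0 whatever p is. It follows that:

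all-patients numerator = normal/missing numerator + 0.

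This assumes that baseline status is judged on the threshold alone. No single value is both above c and at or below c, so the full rule could not classify any baseline as abnormal.

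**Step 2. Which rises are counted across tiers.** All pairs (b, p) from 0.5 to 30 x ULN in steps of 0.1 were tested. The counts describe what the rules allow; they are not expected patient numbers.

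| Analyte | Flagged in a tier with b above that tier's cut-off | Any rise from above the lowest tier, flagged in some tier | Rise to at least 2b from above the lowest tier, flagged |
|---|---|---|---|
| ALT/AST | 0 in all 5 tiers | 27,700 of 39,060 (71%) | 16,900 of 16,900 |
| CPK | 0 in all 3 bands | 15,000 of 36,315 (41%) | 11,900 of 14,400 (83%) |
| Total bilirubin | 0 in both tiers | 1,400 of 40,470 (3.5%) | 1,325 of 18,225 (7.3%) |
| ALP | 0 in its one tier | 0 of 40,470 | 0 of 18,225 |

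The ALT/AST doubling result is general. Successive cut-offs are at most a factor of 2 apart (3/2, 5/3, 10/5, 20/10), so a doubling from any b above 2 and up to 20 x ULN passes the next cut-off. For bilirubin, only baselines above 1.5 and up to 2 x ULN can still be flagged.

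**Step 3. Examples (x ULN).**

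- ALT 2.5 to 6: counted in the 3 and 5 tiers. ALT 2.5 to 2.9: not counted.
- CPK 4 to 8: counted. CPK 4 to 4.9 and 12 to 25: not counted.
- ALP 1.6 to 3.2: not counted.
- Combined criterion, later ALT 6 and bilirubin 3: counted from a baseline of 4 and 1, not from 4 and 2.5.

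**Step 4. Denominator.** If m patients newly cross a cut-off, n are assessed and k started above it, the plan reports m/n; the at-risk proportion is m/(n − k). The planned arms are 38 and 19. The documents do not give k, so 1 to 4 is assumed for illustration, with m = 1:

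- n = 19: 1/19 = 5.3%, against 1/18 = 5.6% to 1/15 = 6.7%.
- n = 38: 1/38 = 2.6%, against 1/37 = 2.7% to 1/34 = 2.9%.

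The dilution is small. One uncounted patient is itself 2.6% or 5.3% of an arm.

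**The case against.** The strongest case on the other side has four parts.

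- **The clause is deliberate.** SAP 5.8 speaks of treatment-emergent PCSVs, and a baseline condition makes each tier count new occurrences. Dropping it would count a stable ALT of 2.1 x ULN as an event. This stands as a reason to keep the clause somewhere, but not as a reason to keep rows that contradict it.
- **The zero depends on how abnormal is read.** If it means above the lowest tier for the parameter, ALT 2.5 to 6 x ULN would appear in the abnormal-baseline row of the 3 and 5 tiers. SAP 5.8.3 does not settle this. The objection stands for multi-tier analytes. ALP has one tier and fails under either reading.
- **Eligibility limits the reach.** With ALT, AST and CPK above 3 x ULN excluded at screening, an abnormal CPK baseline needs a rise before dosing, and the ALT/AST gap is mainly a baseline of 2 to 3 x ULN that stays at or below 3. Investigators may also exclude clinically significant abnormalities. This stands, and it leaves ALP and bilirubin as the most exposed.
- **Other outputs show the data.** The eDISH plot and Hy's law listing have no baseline condition, values and changes are tabulated by visit, and protocol 9.4.3 requires rapid reporting of ALT or AST at least twice an elevated baseline. This covers much of ALT and bilirubin. It does not identify isolated ALP or CPK worsening, and visit summaries do not identify patients.

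A reader might infer that no worsening from a high baseline is ever counted, or that every liver criterion has this flaw. The documents support neither: higher tiers catch many rises, conjugated bilirubin has no baseline clause, and the combined criterion needs only one baseline within its limit.

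**Conclusion.** The inconsistency between SAP 5.8.3 (with protocol 10.4.4.2) and SAP Appendix 10.4 is real. Tier by tier, the abnormal-baseline row for ALT, AST, ALP, total bilirubin and CPK is zero by construction, and the all-patients row only repeats the normal/missing count over a wider denominator. The worsening that escapes every tier is:

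- ALP: any rise from a baseline above 1.5 x ULN.
- Total bilirubin: any rise from above 2 x ULN, and rises that stay between 1.5 and 2 x ULN.
- ALT, AST and CPK: rises that stay within a tier or start above the top one.

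This is a reporting defect that should be corrected; it does not touch patient management or efficacy. A reader might also infer that hepatic signals would be missed altogether. The baseline-free ALT and bilirubin outputs and the protocol's ALT/AST reporting rule do not support that.

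The zero rows for multi-tier analytes rest on the per-tier reading of abnormal; the ALP result does not. The number of affected patients cannot be derived from the documents.

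**What to change.** Reconcile SAP 5.8.3 with Appendix 10.4 before the first-step database lock, by one of two routes:

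1. Apply the threshold without the baseline clause in the all-patients and abnormal-baseline rows and in the PCSV listing.
2. Keep the clause, use at-risk patients (baseline at or below the cut-off) as the denominator, and replace the abnormal-baseline row with a baseline-to-worst-value shift table for ALT, AST, ALP, total bilirubin and CPK.

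In either case, state whether abnormal is judged per tier or per parameter. Add no multiple-of-baseline threshold for ALP, bilirubin or CPK, since the documents contain none.

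The cost is SAP wording and a small programming change, with no new data. Under route 1, stable high values will also enter the all-patients count, so it mixes existing with new abnormalities. Route 2 avoids this.
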